6.0 STATISTICAL PLAN

This proposed sample size is small enough to feasibly recruit over the given time period, yet large enough to correlate differences between the two groups.

Data Cleaning and Crosschecking:

Data cleaning and crosschecking will be conducted prior to analyses. These procedures will include: 1) Comparing patient counts with accrual records; 2) Grouping data by assessment and ensuring a match with the designated number of assessments; 3) Cross-checking baseline and follow-up assessment dates; 4) Ensuring correct questionnaire count match to electronic data fields; 5) Summarizing missing data and checking for definable patterns.

Statistical Analysis:

This study has the primary objective of comparing outcome measures between the MP and PS knee prostheses. We will calculate descriptive statistics for the patient characteristics and measures obtained from each group (means, SD, range). We will use the Shapiro-Wilk test to identify whether each continuous variable fits a normal distribution. We will then use a two-tailed Student's t test for parametric data or the Mann-Whitney U test for nonparametric data to compare the two cohorts. The Pearson χ^2 or Fischer's exact test will be used for categorical variables where appropriate. The level of significance will be defined at $p < 0.05$.

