Stability of the Medial Pivot Total Knee Prosthesis

PRINCIPAL INVESTIGATOR:

[name]
Department of Orthopaedic Surgery
[name]
[name]

SUB-INVESTIGATORS:

[name]
University of Chicago

[name]
Northwestern University

[name]
Northwestern University

[name]
Northwestern University

[name]
Northwestern University

PARTICIPATING SITES:

Northwestern Memorial Hospital

Synopsis

Title	Stability of the Medial Pivot Total Knee Prosthesis
Short Title	Medial Pivot Knee Stability
Protocol Date	04/08/2016
Study Duration	2 years
Study Center(s)	Northwestern Memorial Hospital, Northwestern Memorial Faculty Foundation, Northwestern University
Objectives	To compare objective and subjective measures of knee stability following total knee arthroplasty with a medial pivot design vs. a posterior stabilized design
Number of Subjects	100 (50 in each group)
Diagnosis and Main Inclusion Criteria	Patients requiring total knee arthroplasty that present to Northwestern Memorial Hospital or to [name] or [name] clinic

TABLE OF CONTENTS

Synopsis.....
1.0 Introduction.....
2.0 Study Objectives.....

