5.0 STUDY DESIGN & METHODS

50 patients will be recruited over 12-18 months. Half of the patients will receive the Medacta GMK Sphere prosthesis (Ball-and-socket), while the other half will receive the Medacta GMK posterior stabilized prosthesis (Cam-and-post). Patients will be randomized in the operating room through the opening of opaque, study-numbered envelopes prior to skin incision.

Patient-reported outcomes will be administered pre-operatively, immediately post-operatively, 6 weeks post-operatively, 3 months post-operatively, 6 months post-operatively, 12 months post-operatively, and 2 years post-operatively. Patient-reported outcomes will be measured using the Oxford knee score (see appendix 1), Knee Society Score, VR-12 (see appendix 2), the Forgotten Joint Score (FJS) for the knee (see appendix 3), and the Kujala Scoring Questionnaire (see appendix 4) as well as the physical function, pain interference, and pain behavior PROMIS CATs (see appendix 5). These questionnaires will be completed at the routine post-operative clinic visits or over the phone through PROMIS Assessment Center. The Forgotten Joint Score (FJS) will only be administered at the subject's 12 month post-operative time point and the Kujala Scoring Questionnaire will only be administered at the subject's 2 year post-operative time point.

At 3-6 months post-op, the operative knee will be examined by a single Sports Orthopaedics attending surgeon [name], who is an expert in assessing knee stability. The attending will grade the stability of the knee in various degrees of flexion according to section 4 of the International Knee Documentation Committee's Knee Ligament Standard Evaluation Form (see appendix 3). KT1000 arthrometer (MEDmetrics, San Diego, CA) measurements will also be taken by a single provider at the 3-month postoperative visit. The patient will also be graded on the get-up-and-go test at this time.

A prospective chart review will be performed starting at the time of enrollment and ending at the study completion date to obtain and verify the following data from NMH Medical records (PRIMES, Cerner PowerChart) and NMFF Medical Records (EpicCare, IDX/GE Centricity):

- EPIC Number
- MRN
- Medical History
- Medications
- Surgical History
- Date of Surgery
- Time taken to complete surgery
- Type of implant

- Post operative quality of prosthesis position/fixation
- Pre and post-operative lab values (Hg, plts, WBC, ESR, CRP, INR, etc)
- Complications/Reoperations

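### As Section 6.0 is written, a 2-year comparison of the repeated scores ignores the earlier scores of patients missing at 2 years, so the between-arm difference can be biased and loses precision

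*Combined protocol and SAP*

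**What the plan says.** Section 5.0 schedules the patient-reported outcomes before surgery, immediately after it, at 6 weeks and 3 months, and then at "6 months post-operatively, 12 months post-operatively, and 2 years post-operatively". The Oxford, Knee Society, VR-12 and PROMIS scores are therefore repeated measures with up to six assessments before the 2-year one. There are two exceptions: the Forgotten Joint Score is given only at 12 months and the Kujala questionnaire only at 2 years. Questionnaires may be completed in clinic or by phone.

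For continuous outcomes, Section 6.0 says: "We will then use a two-tailed Student's t test for parametric data or the Mann-Whitney U test for nonparametric data". The significance level is 0.05. Missing data appear once, as the last data-cleaning step: "Summarizing missing data and checking for definable patterns". The documents contain no repeated-measures model, imputation, baseline adjustment, analysis population, sensitivity analysis or allowance for dropout.

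**The concern.** A two-sample test takes one value per patient. A patient who scores badly at 6 and 12 months and has no 2-year score adds nothing to a 2-year test, although the earlier scores show how that knee was doing. The plan expects missing data, since it sets out to summarise them, but attaches no action to what it finds.

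Two things are at stake. If patients with poor scores are more likely to be lost, those who remain look too good. When one implant truly gives worse scores, its arm loses more of its poor results and the observed difference shrinks. When the link between score and dropout exists in one arm only, a difference can appear where there is none. Separately, unused earlier scores mean lost precision in a small trial. Leaving the method open also lets it be chosen after the data are seen.

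**Working it through.** **Inputs from the documents.** Two-sided alpha is 0.05 and allocation is 1:1. The Synopsis gives "100 (50 in each group" and Section 5.0 gives "50 patients will be recruited over 12-18 months", so both 50 and 25 per arm are shown. There is no stated calculation to reproduce: the sample size rests on being feasible "yet large enough to correlate differences between the two groups", with no effect size, SD, power or loss rate.

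**Assumed inputs.** Scores have SD 1. The correlation r between an earlier score and the 2-year score is 0.5 or 0.7. Loss is 10-30%. Where dropout depends on the score, it is logistic with a log-odds slope of 1.0 or 1.5 per SD.

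**Step 1: what the trial can detect.** At 80% power the detectable difference is (1.96 + 0.84) x sqrt(2/m), for m patients analysed per arm.
- 50 per arm: 0.56 SD. With 20% missing (m = 40): 0.63 SD. Power for 0.5 SD falls from 70.5% to 60.9%.
- 25 per arm: 0.79 SD. With 20% missing (m = 20): 0.89 SD. Power falls from 42.4% to 35.2%.

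**Step 2: large-sample bias.** If dropout depends only on the earlier score, the error in an arm's observed 2-year mean is r x (mean earlier score of those who stay - mean earlier score of all). With slope 1.0 and 20% loss the shift in brackets is 0.174, so the arm error is 0.7 x 0.174 = 0.122, or 0.5 x 0.174 = 0.087. Simulation with 1,000,000 patients per arm gives 0.121-0.122 and 0.087. For the between-arm difference at r = 0.7:
- Same rule, no effect: 0.122 - 0.122 = 0. The arm means are too high by the same amount.
- Same rule, true effect 0.5 SD: the better arm loses 14% and its shift is 0.122, against 0.173 in the other arm, so 0.7 x (0.122 - 0.173) = -0.036 (simulated -0.035).
- Score-dependent dropout in one arm only, equal rates: 0.7 x (0 - 0.174) = -0.122 (simulated -0.120 to -0.122).

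Over 10-30% loss and both correlations, the second case gives 0.015-0.046 SD of attenuation and the third 0.045-0.178 SD of bias. An estimator that uses the earlier score gives about 0.00 in all three.

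In the third case with no true effect and r = 0.7, type I error is about 6.7% (25 per arm) or 8.5% (50 per arm) at 20% loss, and 8.2% or 11.4% at 30% loss.

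**Step 3: trials of the planned size.** The set-up was 20,000 simulated trials, true difference 0.50 SD, r = 0.7, same rule in both arms. The likelihood estimate regresses the 2-year score on the earlier score in completers and predicts at the mean earlier score of all patients.

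| Slope | Loss by arm | Per arm | Observed cases | Likelihood |
|---|---|---|---|---|
| 1.0 | 27% vs 19% | 25 | 0.456 | 0.499 |
| 1.0 | 27% vs 19% | 50 | 0.454 | 0.497 |
| 1.5 | 30% vs 20% | 25 | 0.426 | 0.498 |
| 1.5 | 30% vs 20% | 50 | 0.429 | 0.502 |

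At 25 per arm the shrinkage is (0.50 - 0.456)/0.50 = 9% and (0.50 - 0.426)/0.50 = 15%.

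**Step 4: precision.** Under 20% random loss at 25 per arm, the SD of the estimate falls from 0.3137 to 0.2977. The variance ratio is (0.2977/0.3137)^2 = 0.90.

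**Step 5: dropout that depends on the unobserved 2-year score.** With 20% loss and r = 0.7, bias falls only from 0.174 to 0.094 (one arm only), or from 0.051 to 0.029 (same rule, 0.5 SD effect). More than half remains: 0.094/0.174 = 54% and 0.029/0.051 = 57%.

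**The case against.** **A reader might infer that loss of poor responders necessarily biases the 2-year comparison.** It does not. Step 2 gives zero bias in the difference when the dropout rule is the same in both arms and there is no effect. With the same rule and a true effect, the error shrinks a real difference and creates no false one. False positives need a dropout pattern that differs by arm, and nothing in the documents points to one.

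**A reader might infer that the plan tests at every visit and excludes patients who withdraw.** Section 6.0 says neither; its wording is only "or the Mann-Whitney U test for nonparametric data to compare the two cohorts". Observed-case analysis is the default that follows from the tests named, not a stated rule.

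**The bias is small against sampling error.** A bias of 0.04-0.07 SD sits inside a sampling SD of about 0.22-0.32, and the observed-case 95% interval still covers at 94-95%. With separate regressions by arm at 25 per arm, the root mean squared error is 0.318 (observed cases) against 0.313 (likelihood) at slope 1.0, and 0.324 against 0.325 at slope 1.5, which is no gain. The objection holds for that estimator but not for a covariance pooled across arms. Pooling gives 0.306 against 0.319 and 0.307 against 0.320 under score-dependent dropout (mean squared error down about 8% in each), and 0.303 against 0.320 under 20% random loss.

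**The model is heavy for the sample.** Seven assessments with an unstructured covariance need 7 x 8/2 = 28 parameters; six with the pre-operative score as a covariate need 6 x 7/2 = 21. With possibly 25 patients per arm this stands, so a fallback must be fixed in advance. The simulations used two time points and do not test a full seven-assessment model.

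**Other points that stand.** Phone completion may keep loss below the assumed rates. The Kujala and Forgotten Joint scores have no earlier value on the same instrument, so the model does not help them. A normal-theory model also sets aside the plan's provision for non-normal scores unless the rank test is kept.

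**Conclusion.** The point holds as a conditional one. For the Oxford, Knee Society, VR-12 and PROMIS scores, the named tests leave earlier data unused, and the 2-year difference can be biased; the documents do not support saying that it is biased. With a true difference of 0.50 SD, a correlation of 0.7 and 19-30% loss under one dropout rule, the observed-case estimate is about 0.43-0.46 SD. The precision gain, about 10% of variance under 20% random loss, needs no bias mechanism.

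All loss rates, slopes and correlations are assumptions. The bias correction also requires that dropout depend on observed scores; otherwise only part of the bias is removed. The expected effect is modest, but so is the cost, and the change is worth making before the data are seen.

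**What to change.** For the four repeated scores only, amend Section 6.0 as follows.
- **Main analysis.** A likelihood mixed model for repeated measures on all randomised patients and all available visits, with group, visit, group-by-visit and the pre-operative score, and one covariance common to both arms. Read the group difference at 12 months and 2 years from it.
- **Fallback.** Name in advance the simpler covariance, or the reduced set of visits, to be used if the unstructured form does not converge. State how a missing pre-operative score is handled, because a covariate with no value would otherwise remove the patient.
- **Sensitivity analyses.** Keep the planned t or Mann-Whitney test on observed cases, which also covers non-normal scores. Add one analysis in which dropout depends on unobserved scores, for example by shifting the missing 2-year values by stated amounts in each arm.
- **Kujala and Forgotten Joint scores.** Leave the planned tests in place and report missingness by arm.

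The cost is SAP wording and a standard model, with no new visits or data. The downside is reliance on dropout that depends on observed scores and on approximately normal residuals. The Synopsis and Section 5.0 should also be reconciled on the number of patients, since that decides how rich a covariance the trial can support.

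### The pre-operative patient-reported scores have no role in the planned group comparison and no between-group difference with a confidence interval is planned: a cheap, optional gain in precision

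*Combined protocol and SAP*

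**What the plan says.** In section 6.0 (Statistical Plan) of the combined protocol and SAP the method is chosen by a normality test: "We will use the Shapiro-Wilk test to identify whether each continuous variable fits a normal distribution". The comparison is then a "t test for parametric data or the Mann-Whitney U test for nonparametric data to compare the two cohorts", two-tailed, at the 0.05 level. No covariate, change score or model is named. Baseline appears in that section only as a date check during data cleaning. The planned summaries are "descriptive statistics for the patient characteristics and measures obtained from each group (means, SD, range"), with no between-group difference or confidence interval.

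Section 5.0 (Study Design & Methods) gives the timing: "Patient-reported outcomes will be administered pre-operatively, immediately post-operatively, 6 weeks post-operatively", then at 3, 6 and 12 months and 2 years. This schedule covers the Oxford, Knee Society, VR-12 and three PROMIS scores. Allocation comes later: "Patients will be randomized in the operating room through the opening of opaque, study-numbered envelopes prior to skin incision". The pre-operative scores can therefore be used as pre-randomisation covariates.

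Other outcomes have no such score. "The Forgotten Joint Score (FJS) will only be administered at" 12 months, Kujala is given only at 2 years, and KT1000 "measurements will also be taken by a single provider at the 3-month postoperative visit". On sample size, section 5.0 says "50 patients will be recruited over 12-18 months", half to each prosthesis, while the Synopsis says 100, 50 per group. That conflict is a separate matter; both sizes are carried through below.

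**The concern.** A patient's score before surgery usually predicts part of the score after it. In a randomised trial, adjusting for it removes that part of the variance from the treatment comparison without introducing bias. Here the scores are already collected, the sample is 50 or 100, and section 6.0 gives no effect size, SD or power, so unused prognostic information deserves attention.

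Reporting is also at stake. With intervals as wide as those computed below, a non-significant p value would not show that the two knees perform alike, and the plan does not commit to printing the figure that would make this visible. Moreover, if Shapiro-Wilk is applied separately at each visit (the plan does not say), the same score could be compared on means at one visit and on ranks at another.

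**Working it through.** The plan has no power figure to reproduce.

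**Inputs from the documents.** Two-sided 0.05 (section 6.0); 1:1 allocation and n = 25 per arm (section 5.0) or n = 50 per arm (Synopsis).

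**Assumed, because the documents give neither.** A true difference of 0.5 SD, and r from 0 to 0.6. No dropout.

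**Step 1: normal scores.** In SD units, the unadjusted standard error is sqrt(2/n), which is 0.283 (n = 25) or 0.200 (n = 50). For ANCOVA the variance is multiplied by (1 − r²) × [1 + 1/(2n − 4)]; the bracket is the price of estimating the slope. Power is from the noncentral t with noncentrality 0.5/SE, on 2n − 2 df unadjusted and 2n − 3 df adjusted. Example, n = 25 and r = 0.5: 0.75 × (1 + 1/46) = 0.766; SE = sqrt(0.08 × 0.766) = 0.248; noncentrality 2.02; power 50.7%.

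| | 25 per arm | 50 per arm |
|---|---|---|
| Unadjusted | 41.0% | 69.7% |
| ANCOVA, r = 0 | 40.3% | 69.2% |
| ANCOVA, r = 0.3 | 43.5% | 73.3% |
| ANCOVA, r = 0.5 | 50.7% | 81.1% |
| ANCOVA, r = 0.6 | 57.2% | 86.8% |

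The variance gain vanishes below r of about 0.15 (n = 25) or 0.10 (n = 50).

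**Step 2: skewed scores, against the plan's own rule.** This is a simulation with 6,000 trials per cell, beta-shaped follow-up scores, a normal baseline, r on the latent scale, and a 0.5 SD difference. The plan is taken as Shapiro-Wilk at 0.05 on the pooled data, then t or Mann-Whitney (level and pooling are assumed; testing each arm separately changes the plan's power by at most 1.2 points). Power in %, 25 per arm / 50 per arm:

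| Skewness, r | Plan | ANCOVA | Rank ANCOVA |
|---|---|---|---|
| −0.60, 0.3 | 39.4 / 70.5 | 42.4 / 73.2 | – |
| −0.60, 0.5 | 42.0 / 70.2 | 51.4 / 81.1 | 49 / 81 (2,500 trials) |
| −0.81, 0.2 | 44.1 / 74.5 | 42.0 / 70.5 | 46.0 / 75.5 |
| −0.81, 0.5 | 45.0 / 74.9 | 50.9 / 80.3 | 55.2 / 83.9 |
| −1.21 pure shift, 0.2 | 57.5 / 87.0 | 41.9 / 71.4 | 59.7 / 87.7 |
| −1.21 pure shift, 0.5 | 57.6 / 86.6 | 49.2 / 79.5 | 68.0 / 93.5 |
| −1.21 bounded scale, 0.2 | 42.9 / 73.1 | 41.0 / 70.5 | 44.2 / 74.0 |
| −1.21 bounded scale, 0.5 | 43.5 / 73.1 | 49.4 / 79.5 | 53.1 / 83.4 |

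A pure shift moves some scores past the ceiling of a bounded scale. The bounded-scale rows keep scores within it while holding the mean difference at 0.5 SD.

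**Step 3: validity.** With no true difference and r = 0.5 (10,000 trials; normal scores and both stronger skews), rejection rates were 4.5–5.0% for the plan, 4.6–5.4% for ANCOVA and 4.8–5.3% for rank ANCOVA.

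**Step 4: interval width.** The unadjusted 95% half-width is 2.011 × sqrt(2/25) = 0.57 SD, or 1.984 × sqrt(2/50) = 0.40 SD. With ANCOVA at r = 0.5 it is 2.012 × 0.248 = 0.50 SD, or 1.985 × 0.174 = 0.35 SD.

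**The case against.** The strongest reply is that nothing here is wrong. Allocation is randomised, the planned tests hold their error rate, and the gain rests on an r that the documents do not give. At r = 0.3 with normal scores it is about 2.5 points with 25 per arm (43.5 − 41.0) and 3.6 with 50 (73.3 − 69.7). This stands, and it limits the point to efficiency.

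A reader might infer that no between-group interval could be obtained where Mann-Whitney is used. The documents do not support that: the means and SDs are planned for the measures in each group, whichever test follows, and with n they give a mean difference and its interval. Such intervals covered 94.9–95.2% in 40,000 null trials per cell under skewness −0.81 and −1.21. What cannot be derived is a baseline-adjusted interval, or one that matches a Mann-Whitney result. For outcomes without a baseline, the complaint is therefore about presentation.

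A reader might also infer that ANCOVA always wins. The pure-shift rows at −1.21 show otherwise, and a rank analysis kept only for sensitivity would not restore power lost in the main one.

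Finally, the stated objective is knee stability. KT1000 and the IKDC ligament grades have no scheduled baseline on their own scales. Section 5.0 takes pre-operative stability from the chart, but on neither scale. Adjustment gains nothing for these measures, and the proposed intervals cover continuous outcomes only, so IKDC grades keep their categorical test.

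**Conclusion.** The point holds as an optional efficiency gain. Two textual facts are firm: the pre-operative Oxford, Knee Society, VR-12 and PROMIS scores have no stated role in the comparison, and no between-group difference with an interval is planned. The loss is conditional. At r = 0.5 with normal scores it is about 10 points of power with 25 per arm (41% to 51%) and 11 with 50 (70% to 81%), for an assumed 0.5 SD difference. At r = 0 adjustment costs under 1 point.

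Linear ANCOVA gains with normal or mildly skewed scores. Under strong skew the result depends on how the effect acts: at −1.21, r = 0.5 and 25 per arm, it trails the plan under a pure shift (about 58% against 49–50%) and leads on a bounded scale (49% against 44%), though there it trails slightly at r = 0.2 (41% against 43%). Rank ANCOVA matched or beat the plan in the skewed settings.

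A reader might take this as evidence of bias or of an inflated false-positive rate. It is neither: the planned comparison is unbiased under randomisation, and its simulated error rate stayed near 5%.

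**What to change.** Put in section 6.0, under Statistical Analysis:

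> For each score with a pre-operative value (Oxford, Knee Society, VR-12, PROMIS), the follow-up score at 6 weeks, 3, 6 and 12 months and 2 years will be analysed by ANCOVA with randomised group and the pre-operative score as covariate, whatever the Shapiro-Wilk result, and the adjusted difference (MP minus PS) reported with a 95% CI. A missing pre-operative score will be replaced by the mean of the observed pre-operative scores over both groups. A rank-based ANCOVA (ranks of the follow-up score on group and ranks of the pre-operative score) will be reported alongside for every such comparison; it replaces the Mann-Whitney test for these scores and gives their p value where the Shapiro-Wilk test rejects normality. Immediate post-operative scores will be described only. For continuous outcomes without a scheduled pre-operative measurement (Forgotten Joint Score, Kujala, KT1000, get-up-and-go if timed), the planned test stays and the unadjusted between-group difference will be reported with a 95% CI.

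The immediate visit is set apart because all 12 Oxford items and 9 of the 14 printed VR-12 questions (Appendices 1 and 2) ask about the past 4 weeks, which at that visit reaches back before surgery. The missing-score rule is needed because section 5.0 lets patients skip questions.

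Cost: wording and one degree of freedom per model; no new data. Rank ANCOVA loses about 2 points with normal scores at low r (at r = 0, 41.1% to 39.0% with 25 per arm and 69.8% to 68.0% with 50). Under strong skew the linear estimate may be less precise than a rank analysis, and its interval may disagree with the rank p value, so both should be shown. The figures above are for each analysis on its own; the combined rule was not simulated. With 10% of pre-operative scores missing at random and r = 0.5, mean replacement costs about 1.4 points with 25 per arm (50.6% to 49.2%) and 1.3 with 50 (80.9% to 79.6%).

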	ALL OF THE TIME	MOST OF THE TIME	A GOOD BIT OF THE TIME	SOME OF THE TIME	A LITTLE OF THE TIME	NONE OF THE TIME
a. Have you felt calm and peaceful ?	1	2	3	4	5	6
b. Did you have a lot of energy ?	1	2	3	4	5	6
c. Have you felt downhearted and blue ?	1	2	3	4	5	6

7. During the past 4 weeks, how much of the time has your physical health or emotional problems interfered with your social activities (like visiting with friends, relatives, etc.)?

ALL OF THE TIME	MOST OF THE TIME	SOME OF THE TIME	A LITTLE OF THE TIME	NONE OF THE TIME
1	2	3	4	5

Now, we'd like to ask you some questions about how your health may have changed.

8. Compared to one year ago, how would you rate your **physical health** in general now?

MUCH BETTER	SLIGHTLY BETTER	ABOUT THE SAME	SLIGHTLY WORSE	MUCH WORSE
1	2	3	4	5

9. Compared to one year ago, how would you rate your **emotional problems** (such as feeling anxious, depressed or irritable) **now**?

MUCH BETTER	SLIGHTLY BETTER	ABOUT THE SAME	SLIGHTLY WORSE	MUCH WORSE
1	2	3	4	5

3. IKDC Knee ligament standard evaluation form

THE IKDC KNEE LIGAMENT STANDARD EVALUATION FORM *[1]

Name: _____ first name: _____ DOB: ____/____/____ med. rec. #: _____
 Examiner: _____ date of examination: ____/____/____ date of injury/les: ____/____/____ date of surgeries: ____/____/____
 Cause of injury: ADL*[2] traff. non-pivoting non-contact sports pivoting non-contact sp. contact sp. work
 Time inj. to surg. : _____ (months) acute (0-2 weeks) subacute (2-8 weeks) chronic (>8 weeks)
 Knee involved: r. l. opposite knee: norm. injured exam. under anesth.: yes no
 Postop. diagnosis: _____
 Surgical proced.: _____
 Status menisci: norm med. lat. 1/3 removed: med. lat. 2/3 removed: med. lat. compl. rem. med. lat.
 Morphotype: lax normal tight varus valgus
 Activ.level*[3]: preinjury: I II III IV pretreatment: I II III IV
 present: I II III IV Eventual change knee-related: yes no

GROUPS (PROBLEM AREA)	QUALIFICATION WITHIN GROUPS *[4]				GROUP QUALIFC. A B C D*[4]
	A: normal	B: nearly norm.	C: abnormal	D:sev. abnorm.	

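### Section 6.0 names no test specifically for ordered outcomes; on its plain wording the IKDC stability grades get chi-square or Fisher's exact test, which ignore the order

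*Combined protocol and SAP*

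**What the plan says.** Section 6.0 (Statistical Analysis) sets out two routes. For the first: "We will use the Shapiro-Wilk test to identify whether each continuous variable fits a normal distribution". The next sentence gives a two-tailed t test for parametric data "or the Mann-Whitney U test for nonparametric data to compare the two cohorts". For the second, Pearson chi-square or Fisher's "exact test will be used for categorical variables where appropriate". Ordered outcomes are not mentioned, and no outcome is matched by name to a test.

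Section 5.0 makes the IKDC examination a planned stability outcome: "The attending will grade the stability of the knee in various degrees of flexion according to section 4" of the IKDC form. That form, in Appendix 3, is ordered throughout. Its header has a column "GROUP QUALIFC. A B C D", running from normal to severely abnormal. Its section 4 holds seven distinct four-level items, two optional repeat measurements, a firm/soft endpoint and a group grade. The plan does not say which of these is compared between arms.

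**The concern.** The study objective is to compare knee stability, and the IKDC examination is one of two clinic stability measurements. The other, the KT1000 arthrometer, is continuous and already covered. A shift of knees from C and D towards A and B is the kind of difference the trial looks for. Chi-square and Fisher's exact test spread their sensitivity over every pattern of difference between the arms, whereas a rank test concentrates it on a shift along the scale. If the plain wording is followed, a real shift is harder to detect.

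The wording also leaves room to decide after the data are seen whether grades are categorical or nonparametric data. The two routes can lead to opposite conclusions on the same table.

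**Working it through.** **Inputs from the documents.** Significance level 0.05 (Section 6.0); 1:1 allocation (Section 5.0). The sample size is 50 in total in Section 5.0 and 100 in the Synopsis, so both 25 and 50 per arm are used. The plan states no power, effect size or grade distribution, so there is no figure of its own to reproduce.

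**Assumed.** Grade distributions, and a proportional-odds shift with odds ratio (OR) 2 to 4. Each cumulative odds is multiplied by the OR. For 40/35/20/5% and OR 3, the cumulative shares 0.40, 0.75 and 0.95 have odds 0.667, 3 and 19. These become 2, 9 and 57, giving shares 0.667, 0.900 and 0.983, that is 66.7/23.3/8.3/1.7%.

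**One table, two answers.** Take illustrative A/B/C/D counts of 8/9/6/2 and 14/8/3/0 at 25 per arm.

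- Chi-square: the column totals are 22, 17, 9 and 2, so the expected counts are 11, 8.5, 4.5 and 1 in each arm. The statistic is 2 × (9/11 + 0.25/8.5 + 2.25/4.5 + 1/1) = 4.695 on 3 df, p = 0.196. Fisher's exact test gives p = 0.213.
- Mann-Whitney: the midranks are 11.5, 31, 44 and 49.5. The rank sum in the first arm is 92 + 279 + 264 + 99 = 734, against 25 × 51/2 = 637.5 expected. The tie-corrected variance is (25 × 25/12) × [51 − (10626 + 4896 + 720 + 6)/(50 × 49)] = 52.083 × 44.368 = 2310.8. So z = 96.5/48.07 = 2.007, p = 0.045.

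**Power (%).** 10,000 simulated trials per setting, two-sided 0.05, shift towards better grades. Each cell gives chi-square / Fisher / tie-corrected Mann-Whitney.

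| Assumed grades, % | OR | 25 per arm | 50 per arm |
|---|---|---|---|
| 40/35/20/5 | 2 | 14.6 / 16.6 / 24.2 | 29.4 / 31.9 / 44.9 |
| 40/35/20/5 | 3 | 32.8 / 36.9 / 49.8 | 64.3 / 67.1 / 80.6 |
| 40/35/20/5 | 4 | 49.1 / 53.3 / 68.3 | 84.4 / 86.0 / 93.8 |
| 30/40/20/10 | 2 | 15.5 / 16.7 / 24.9 | 30.5 / 31.0 / 45.5 |
| 30/40/20/10 | 3 | 34.1 / 36.7 / 53.1 | 67.0 / 67.7 / 82.8 |
| 30/40/20/10 | 4 | 51.8 / 54.6 / 71.3 | 87.1 / 87.5 / 95.3 |
| 70/25/4/1 | 3 | 21.8 / 24.1 / 33.6 | 40.9 / 48.2 / 58.0 |
| 90/9/0.8/0.2 | 3 | 7.2 / 1.7 / 10.7 | 18.0 / 11.6 / 23.9 |
| 50/35/15 | 3 | 35.4 / 35.0 / 46.1 | 66.0 / 64.8 / 75.8 |
| 60/40 | 3 | 41.2 / not run / 41.2 | 69.2 / not run / 69.2 |

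The Monte Carlo standard error is at most 0.5 points. With four well-used grades (the first six rows) the gain over chi-square runs from 95.3 − 87.1 = 8.2 to 71.3 − 51.8 = 19.5 points. Over OR 2 to 4 it is about 5-12 points with three grades (50/35/15 and 40/40/20) and about 2-7 with 90% grade A. With two grades the two tests reject equally often. For shifts towards worse grades the corresponding gains over chi-square are 7-19, 4-11 and 4-15 points.

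**Type I error.** With three or four grades, tie-corrected Mann-Whitney rejects in 4.4-5.2% of trials under no difference. With two grades, both tests reject in 6.2% (25 per arm) and 5.5% (50 per arm). Running both and keeping the significant one gives about 7-8% with three or four well-used grades. At OR 3 with four well-used grades, chi-square and Mann-Whitney disagree on significance in about 17-22% of trials.

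**The case against.** A reader might infer that Section 6.0 assigns no test at all to the IKDC grades. It does not go that far: grades are categories, and there is a rule for categories. What is absent is a rule that respects order. A reader might also infer that chi-square or Fisher's exact test would be wrong here. Neither is invalid, and nothing in the plan says that both routes will be run and one chosen. The 7-8% describes what the open wording would permit, not what the investigators intend.

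The stronger defence is that Mann-Whitney, described as the test for nonparametric data, was meant to cover grades. The wording can bear that, and then no power is lost. But the sentence follows directly from a normality check on continuous variables, so the plain reading does not lead there. The qualifier in "exact test will be used for categorical variables where appropriate" most naturally settles chi-square against Fisher and supplies no ordinal method.

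Three further objections stand in part.

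- The gain depends wholly on assumptions and is small if nearly all knees are grade A.
- A rank test is less sensitive to differences that are not a shift in one direction. Some alternative Lachman bands in Appendix 3 place looser and tighter knees in the same grade, so ranks there compare degree of abnormality, not laxity.
- Whether the group grade or particular items should lead is the investigators' choice. Likewise, the missing scale for the get-up-and-go test ("The patient will also be graded on the get-up-and-go test at this time") is a gap in outcome definition. It does not show that a wrong test is planned.

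**Conclusion.** The point holds as a minor one: avoidable loss of power on the plain reading, and a test choice left open on the wider one. The size rests on assumed grade distributions and a proportional-odds shift, because the documents supply neither. It ranges from nothing (two grades in use, or Mann-Whitney already intended) to about 20 points over chi-square (four well-used grades, shift to better grades). No error in either test used alone is claimed.

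Nor would the change make up for a small trial: at OR 2 with 25 per arm and four well-used grades, Mann-Whitney still has only 24-25% power.

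**What to change.** State in Section 6.0 that the ordered IKDC section 4 grades are compared between arms by a two-sided tie-corrected Mann-Whitney test. Keep chi-square or Fisher's exact test for nominal and two-level variables, such as the firm/soft endpoint. State in advance which section 4 variable, the group grade or named items, is the main IKDC comparison; that choice is the investigators'.

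Do not add a switch to an exact version of Mann-Whitney when expected counts are small. The tie-corrected test already holds its level in the three- and four-grade settings examined, and the switch costs power. At 90% grade A, OR 3 and 25 per arm, a rule that switches when any expected count is below 5 has 1.7% power, against 10.7% for the tie-corrected test and 7.2% for chi-square.

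The cost is a few sentences, using a test the plan already names, with no change to visits, data or staff. The price is the lower sensitivity to non-monotone differences. Where the shared Lachman bands are used, the report should say that the comparison is of abnormality.
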